9.4 STATISTICAL ANALYSES

9.4.1 GENERAL APPROACH

Aim 1. Using descriptive statistics (e.g., frequency, percentage, means, SDs), we will summarize enrollment and retention rates, and proportion of intervention sessions the participants attended. We will measure fidelity of the intervention ($\geq 80\%$ attendance; delivery of $>80\%$ of content) using the process evaluation guide, and assess participant satisfaction with the study and the intervention using the exit interview.

Aim 2. We will use an intent-to-treat approach. Because random assignment is by group and not individually, we will examine potential systematic differences closely between the two groups, comparing baseline characteristics using the Student's t-test or Mann-Whitney test for continuous variables and Chi-square or Fisher's exact test for categorical variables. We will assess change in primary and secondary outcomes in the intervention and control group using the Student's t-test or Mann-Whitney test for continuous variables and Chi-square or Fisher's exact test for categorical variables.

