Phase* or Stage: Cluster randomized controlled with an experimental and wait-list control group.

Description of Sites/Facilities Participants recruited from community sites in Durham, Wake, Orange, Alamance, and Lee Counties in North Carolina.

Enrolling Participants:

Description of Study Intervention/Experimental Manipulation: An experimental group of women receive an intervention consisting of *Su Corzaón Su Vida* education sessions, group physical activity, stress management, and coping skills training. The wait-list control group is offered the intervention at the end of Time 3 (12 months).

[figure not shown]
Manipulation:

Study Duration*: A total of 4 years or 48 months.

Participant Duration: Each participant will be in the study a total of 12 months.

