2.3 RISK/BENEFIT ASSESSMENT

2.3.1 KNOWN POTENTIAL RISKS

Risks to Human Subjects

Institutional Review Board (IRB) approval was obtained from The University of North Carolina at Chapel Hill (UNC-CH). Using a cluster randomized two-group, repeated measures experimental design, the goal of the study is to investigate the feasibility and initial efficacy of a 12-month intervention consisting of: **Phase I**) 12-week nutrition and exercise education, physical activity group sessions, coping skills training, and stress management intervention in perimenopausal Latinas; **Phase II**) 6 months of continued monthly contact to help women improve health behaviors and self-efficacy; and **Phase III**) 6 months of health maintenance without contact from study staff. We will partner with community centers to enroll women and we will partner with two churches in two North Carolina counties to deliver the intervention.

Inclusion criteria include age 40-60 years; self-identify as Latina; understand spoken English or Spanish; perimenopausal (menstrual bleeding in the past three months, but timing of periods have varied in past year, or no menstrual bleeding in the past 3-11 months) or early postmenopausal (1-2 years since final menstrual period); intact uterus and at least one ovary; not currently pregnant; no hormone therapy or oral contraceptives in the past three months. Potential participants will fill out a health history questionnaire to ascertain if they have a history of CVD (heart attack, stroke, coronary heart disease), heart murmur, congenital heart disease, family history of sudden death, difficulty walking or exercising. Women who answers yes to any of these health history questions will be excluded from the study and referred to a health care provider. After enrollment and baseline assessment, two churches in two counties will be randomly assigned to either the intervention or control group. Participants will be assigned to the group in their respective county. Participants will be informed of their group assignment by telephone.

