5.5 STRATEGIES FOR RECRUITMENT AND RETENTION

Procedures for Minority Recruitment and Enrollment and Challenges

This study builds on established partnerships between UNC-CH, local churches, and community centers in Orange County and Durham County. [name] and [name] have extensive experience working with these communities in prior studies, and will guide my community engagement. To assure that we meet enrollment targets, all project staff will be bilingual (English, Spanish) and all study materials (recruitment, intervention, and instruments) will be available in Spanish. Participants will be recruited by a Community Health Worker (CHW) and Research Assistant (RA) from local churches, and community centers in Orange County and Durham County. Two months before enrollment, the Project Coordinator will meet with staff at the churches and community centers to confirm recruitment strategies and place Spanish language flyers with information about the study and eligibility criteria in the entrance and common areas. The flyers will contain a phone number for individuals to call if they're interested in participating in the study. Additionally, the CHW and RA will be available weekly after church services and monthly at events organized by community centers. RAs will record the names and

telephone numbers of interested women privately and schedule them for a phone screening. This approach worked well in prior studies that enrolled 56 women in over a month [42]. We plan to enroll 8-10 women per week and can extend the timeline for enrollment if needed. If we have difficulty enrolling participants we will ask community leaders from the recruitment sites for advice. The Project Coordinator will conduct a phone screening, asking women for their birthdate, last menstrual period, regularity of menstrual periods, history of hysterectomy or oophorectomy, use of hormone therapy or birth control pills, and history of CVD. Women who meet the study criteria will be scheduled for a baseline visit to confirm eligibility, review the study, requirements of participants, and the risks and benefits of participating, random assignment and answer questions. Data collection will occur in a private location in the participant's home (approximately 90 minutes). We have time in the schedule for make-up data collections.

Procedures for Minority Retention and Challenges

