6 STUDY INTERVENTION(S) OR EXPERIMENTAL MANIPULATION(S)

6.1 STUDY INTERVENTION(S) OR EXPERIMENTAL MANIPULATION(S) ADMINISTRATION

6.1.1 STUDY INTERVENTION OR EXPERIMENTAL MANIPULATION DESCRIPTION

Intensive Intervention

The intensive intervention consists of 12 weekly bilingual (English, Spanish) sessions that include 60 minutes of interactive learning, 45 minutes of physical activity, and a 15-minute stress management session. The first 8 sessions will integrate education from SCSV related to CVD risk awareness, healthy food choices, physical activity, blood pressure control, and diabetes. To enhance the relevance of the curriculum to perimenopause, we will include messages from American Heart Association Go Red Por Tu Corazón. Each week CHWs will give participants a SCSV or AHA Go Red Por Tu Corazón handout with information on healthier meals and increasing daily physical activity. In the remaining four learning sessions of Phase I, we will integrate previously tested and acceptable coping skills training sessions (i.e., goal-setting, problem-solving, cognitive restructuring, conflict resolution, assertiveness training) with a focus on barriers for perimenopausal Latinas. Trained bilingual CHWs will deliver learning sessions and 15-minute stress management sessions in groups of 20 participants.

Physical activity classes will be held for 45 minutes after the intensive intervention classes and will include a warm-up and then activities such as Zumba, Kick Boxing, walking, use of light weights and stretch bands, and a cool-down. A bilingual physical activity interventionist certified by the American College of Sports Medicine will teach the physical activity classes and reinforce ways to increase physical activity and decrease sedentary behaviors. At baseline, we will give participants an accelerometer and the RA will train them in its use as part of the intervention. The intervention group will be encouraged to increase their physical activity weekly by small increments until they are averaging 10,000 steps a day or 150 minutes per week; this group will also be provided information on the sociocultural and built environments such as a list of grocers where they can access healthy affordable food and free or low-cost spaces to exercise (e.g., YWCA/YMCA) close to home. Missed physical activity sessions will not be made up, but participants can make up learning and stress management sessions.

Continued Support

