6.3 MEASURES TO MINIMIZE BIAS: RANDOMIZATION AND BLINDING

After enrollment and baseline assessment, the two churches will be randomized to either the intervention or wait-list control group using a computer-generated randomization table. Participants will be informed of their group assignment by telephone. Data collection research assistants will be blinded to group status.

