9.2 SAMPLE SIZE DETERMINATION

Sample size will be limited by available resources. Prior clinical trials among Latinas in North Carolina have enrolled 80-184 women successfully with <20% attrition [45]; therefore, enrollment of 80 women is realistic and achievable. Prior interventions in stress management [46] and exercise plus nutrition education [47] observed a change in systolic BP of 6mmHg (SD \pm 11); our sample of 80 participants will yield 70% power to detect a change this large. This pilot study is effectively a cluster-randomized trial with two groups. Because we have two groups, the pilot is not sufficient for the estimation of intraclass correlation of change in outcomes, so we do not use traditional analysis methods for cluster-randomized trials. We can however, use baseline data to estimate potential variability between clusters, which will be helpful in the estimation of the number of clusters/cluster size required for the fully-powered clinical trial.

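### With one church per arm, the individual-level tests of change assume no between-church variance in change, so their p-values cannot be shown valid as evidence of efficacy

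*Combined protocol and SAP*

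**What the plan says.** Section 6.3 states that "the two churches will be randomized to either the intervention or wait-list control group". Section 2.3.1 adds that "Participants will be assigned to the group in their respective county". There is therefore one cluster per arm, with 40 women planned in each (Section 9.1).

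Section 9.2 recognises the design as in effect cluster-randomised and reasons that "the pilot is not sufficient for the estimation of intraclass correlation of change in outcomes, so we do not use traditional analysis methods". It also states that "our sample of 80 participants will yield 70% power to detect a change this large", the change being 6 mmHg in systolic blood pressure with SD 11. It plans to use baseline data on variability between clusters in sizing the full trial.

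Section 9.4.1 acknowledges that assignment is by group and responds with a comparison of baseline characteristics. It then says: "We will assess change in primary and secondary outcomes in the intervention and control group using the Student's t-test or Mann-Whitney test". Chi-square or Fisher's exact tests cover categorical outcomes. Sections 9.4.2 and 9.4.3 refer back to it, and Section 9.4.6 presents the 6-month comparison as an analysis of the intervention's effect. Section 9.3 would add imbalanced baseline variables as covariates in models, and Section 2.3.1 mentions general linear mixed models for testing the hypotheses.

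Section 9.1 says the pilot will assess the feasibility and validity of the trial plan descriptively and is not meant to test the main trial's hypotheses. Initial efficacy is nonetheless part of the primary objective (Sections 1.1 and 3).

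**The concern.** With one church per arm, anything that makes one church's women change differently from the other's appears in full as an arm difference. Examples would be a local health campaign, a change in clinic access, or a different season of measurement. The planned tests compare that difference with the variation among women within a church, and so set the between-church variance in change to zero.

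That the ICC cannot be estimated is a reason to withhold efficacy p-values. Section 9.2 uses it as a reason to analyse as if the ICC were zero.

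The other safeguards do not help. Baseline comparisons and covariates deal with measured baseline characteristics, not with an unmeasured church-level change during follow-up. A mixed model cannot separate a church effect from arm when each arm has one church.

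The stake is that a nominally significant result could be reported as initial efficacy when it is a church effect, and nothing in the data could show otherwise.

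**Working it through.** **Inputs from the documents.** Two churches, one per arm (2.3.1, 6.3); 40 women per arm (9.1); 6 mmHg, SD 11, stated power 70%, attrition below 20% in prior trials (9.2). A 20% loss leaves 0.8 × 40 = 32 per arm.

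**Assumptions.** Alpha 0.05, two-sided unless noted; ICC of change 0 to 0.05; normally distributed change with one random church effect per arm. The documents give none of these.

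**1. The plan's 70% power at ICC 0.** Power ≈ Φ(6 / SE − z), with SE = 11 × √(2/m).
- 40 per arm, two-sided: SE = 2.46, 6/2.46 = 2.439, Φ(2.439 − 1.960) = 68.4% (67.3% by noncentral t).
- 32 per arm, one-sided: SE = 2.75, 6/2.75 = 2.182, Φ(2.182 − 1.645) = 70.4% (69.6% by t).
- 32 per arm, two-sided: 58.8% (57.5% by t).

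The stated figure fits more than one basis. Both bases that come close set the ICC to zero.

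**2. Power if the ICC were known and allowed for.** Multiply the variance by the design effect 1 + (m − 1) × ICC. With m = 40 this is 1.39, 1.78 and 2.95 at ICC 0.01, 0.02 and 0.05.
- 40 per arm, two-sided: 54.3%, 44.8%, 29.5%.
- 32 per arm, one-sided: 60.3%, 52.8%, 39.0%.

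**3. True type I error of the planned t-test.** With m women per church the t statistic is inflated by f = √(1 + m × ICC / (1 − ICC)). The two-sided error is 2 × P(T > t₀.₉₇₅ / f) on 2m − 2 degrees of freedom. Example, m = 40 and ICC 0.01: f = √(1 + 0.40/0.99) = 1.185; 1.991/1.185 = 1.680; error = 9.7%.

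| ICC of change | 40 per church, two-sided | 32, two-sided | 40, one-sided | 32, one-sided |
|---|---|---|---|---|
| 0 | 5.0% | 5.0% | 5.0% | 5.0% |
| 0.001 | 5.5% | 5.4% | 5.3% | 5.3% |
| 0.01 | 9.7% | 8.7% | 8.2% | 7.6% |
| 0.02 | 14.4% | 12.5% | 11.0% | 9.9% |
| 0.05 | 26.2% | 22.7% | 17.4% | 15.6% |

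Simulation of 40,000 trials per setting agrees with the two-sided columns to within about 0.3 points. The Mann-Whitney test behaves much the same: 9.5% at ICC 0.01 and 24.1% at 0.05 with 40 per church (5,000 simulated trials).

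Section 6.1.1 delivers "15-minute stress management sessions in groups of 20 participants", which may add clustering in the intervention arm. An added group ICC of 0.01 for two such groups raises 9.7% to about 11%.

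**4. No valid cluster-level test exists here.** A test on church means has 2 − 2 = 0 degrees of freedom. A randomisation test has two possible allocations, so its smallest p-value is 1.0 two-sided or 0.5 one-sided.

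**5. Baseline ICC from two churches.** The exact F interval has 1 and 78 degrees of freedom. An observed ICC of 0.02 gives F = 1.78/0.98 = 1.816. Dividing by the 97.5% and 2.5% F quantiles (5.223 and 0.000988) and converting by (F − 1)/(F + 39) gives a 95% interval from −0.017 to 0.979. It also concerns baseline levels, not change.

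**The case against.** The strongest reply is that this is a pilot whose limits are largely disclosed. Section 9.2 calls it effectively cluster-randomised and says the ICC cannot be estimated; Section 9.4.1 repeats that assignment is by group; Section 9.1 disclaims testing the main trial's hypotheses. The plan sets no alpha and no rule for declaring efficacy, and the t-test remains meaningful as a comparison of the women in these two churches. Resources, not power, set the sample size. On this view one caveat would be enough.

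Part of this stands. The disclosure is real. The inflation figures depend wholly on assumed ICCs and illustrate the problem without measuring it. The descriptive wording in Section 9.1 is attached to the feasibility and validity of the trial plan, while the same section sets an efficacy comparison as Aim 2, so reporting Aim 2 descriptively extends that wording. The ordinary reading of the power statement is 40 per arm, two-sided, which gives 68.4%.

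The core is not answered. The disclosure neither withdraws the tests nor limits how they may be read. Initial efficacy is in the primary objective, a power figure is quoted, and no text says the p-values hold only if change does not vary between churches.

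**Conclusion.** The concern holds and should be fixed. The p-values for change cannot be shown valid as evidence of efficacy. Calling them invalid would need a known positive ICC, which neither the documents nor the trial can supply. Under the random-church model in the working, any positive ICC takes the nominal 5% test above 5%: to 9.7% at ICC 0.01 and 26.2% at 0.05 with 40 per church, two-sided.

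The 70% power is an individual-randomisation figure. No design effect, alpha or sidedness is stated, nor whether attrition is allowed for. The feasibility aim is unaffected.

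The county question is secondary. Section 1.1 has "Participants recruited from community sites in Durham, Wake, Orange, Alamance, and Lee Counties in North Carolina", whereas Section 5.5 recruits "from local churches, and community centers in Orange County and Durham County" and Section 2.3.1 also speaks of two counties. Arm is confounded with county as well if the two-county rule applies; it is confounded with church in either case.

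**What to change.** - **Sections 9.4.1 and 9.4.6:** report Aim 2 descriptively, giving change by arm with SD and the arm difference, without between-arm efficacy p-values. State that the difference cannot be separated from church.
- **Intervals:** label any interval as ignoring clustering and show it widened at stated assumed ICCs, using the numbers analysed. For systolic blood pressure the half-width is 1.96 × 11 × √(2 × design effect / m). At ICC 0, 0.01, 0.02 and 0.05 this is 4.8, 5.7, 6.4 and 8.3 mmHg with 40 per arm, and 5.4, 6.2, 6.9 and 8.6 mmHg with 32.
- **Section 9.2:** remove the 70% power, or relabel it as assuming individual randomisation (ICC 0) and state its alpha, sidedness and attrition. Report any two-church baseline ICC only with its exact interval, and size the full trial over a range of external ICCs.
- **Sections 2.3.1 and 9.3:** reconcile the mixed models and covariate models with 9.4.1, keeping any model only for descriptive adjusted differences.
- **Sections 1.1, 2.3.1 and 5.5:** reconcile the recruitment counties and state how each woman is linked to a church.

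The cost is wording only, with no extra participants or visits. The pilot gives up p-values whose validity nobody could verify.

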Data will be collected at Time 1 (baseline [0 months]), Time 2 (post Intensive Intervention and Continued Support [6 months]), and Time 3 (6 months after completion of Continued Support [12 months]). Data collected will include the primary outcomes of blood pressure, arterial stiffness based on carotid-femoral pulse wave velocity measures, lipid profile (total cholesterol, high-density lipoprotein, low-density lipoprotein, triglycerides), blood glucose; secondary outcomes of health behaviors (Sleep Quality Questionnaire, Food Behavior Checklist, Physical Activity Questionnaire, and 7-day Accelerometer), self-efficacy (Eating Self-Efficacy Scale and Exercise Self-Efficacy Scale), body mass index, waist circumference, hs-CRP, hair cortisol, and vasomotor symptoms. We will also evaluate the feasibility of the study including, number of eligible participants; methods of identifying/recruiting participants; willingness of participants to be randomized; practicality of delivering the intervention in the proposed setting; enrollment and retention rates, and suitability of the intervention and assessment protocol. Data analysis will use descriptive statistics and general linear mixed models to test the hypotheses. Both intervention and control group participants will each receive \$120 for their time during data collection visits (\$35 at Time 1, \$40 at Time 2, \$45 at Time 3) and \$5 to help with transportation costs each time they come to class or data collection visit.

Participants in the intervention group will receive a 12-week Intensive Intervention (Phase I) with weekly 2-hour sessions consisting of 60 minutes of nutrition and exercise education and coping skills training, a 45-minute physical activity class, and 15-minute stress management session. During Continued Support (Phase II), participants will meet monthly for 3 months for 60 minutes of classroom discussion regarding problems they are having with nutrition and physical activity. Data collection in the wait-list control group will occur at the same time intervals as women in the intervention group. Following the last data collection, we will offer Phase I of the intervention to women in the wait-list control group.

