4 STUDY DESIGN

4.1 OVERALL DESIGN

This study will use a cluster randomized repeated measures study design with two groups to evaluate the feasibility and initial efficacy of the intervention with 80 perimenopausal Latinas. The intervention group (n=40) will receive a 3-phased intervention. In Phase I (Intensive Intervention), bilingual community health workers will meet with women in small groups to deliver 12 weekly (3 months) 2-hour sessions including education, group physical activity, stress management, and coping skills training. Phase II (Continued Support) consists of 3 monthly 1-hour sessions led by community health workers to problem-solve issues related to nutrition and exercise, stress management, and to provide feedback and support. During Phase III (Follow-up), participants are expected to maintain skills on their own for 6 months. Data will be collected at baseline (Time 1), completion of Phase II (Time 2, 6 months after baseline), and after completion of 6 months on their own (Time 3, 12 months after baseline). Data in the wait-list control group (n=40) will be collected at the same time intervals as the intervention group. After Time 3 data collection, they will be offered the Intensive Intervention (12 weekly sessions). Both groups will receive reminders a week prior to each data collection visit and a monthly "thank you" card for their continued participation.

Data will be collected at Time 1 (0 months [baseline]), Time 2 (6 months [completion of the intervention]) and Time 3 (12 months [after 6 months with no contact from the study staff]). Time 2 data will determine the magnitude of the intervention effects after the intensive intervention and continued support; Time 3 data collection will test initial efficacy after participants have had sufficient time to implement their new nutrition, physical activity, and coping skills on their own. We will assess feasibility using questionnaires at Time 3, as well as process evaluations and attendance logs. We chose these times because 6-to-12 months after completion of an intervention is a standard interval for follow-up in behavioral interventions during perimenopause [34].

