9.3 POPULATIONS FOR ANALYSES

Means, standard deviations, minimums, medians, and maximums will be determined for each continuous variable; frequencies and percentages will be tabulated for each categorical variable. Preliminary analyses will be performed to determine whether, despite randomization, the intervention and control groups were unbalanced on age, education, income, or other participant characteristics. Any variable with an imbalance between the groups at baseline will be examined to determine whether it is related to any of the outcome variables. If significant relationships are identified, the variable will be included as a covariate in the models for the affected outcome(s) as a potential confounder. An intent-to-treat analysis will be used in which all subjects are included in the analysis and analyzed according to their initial randomized assignment.

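### Section 9.4.1 tests unadjusted change and does not prespecify adjustment for the outcome's own baseline value; with one church per arm, both estimates should be planned and reported side by side

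*Combined protocol and SAP*

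**What the plan says.** Section 9.4.1 carries the whole outcome analysis, since 9.4.2 (primary endpoints) and 9.4.3 (secondary endpoints) only refer back to it. For continuous outcomes it reads: "We will assess change in primary and secondary outcomes in the intervention and control group using the" Student's t-test or Mann-Whitney test. Categorical outcomes get a chi-square or Fisher's exact test. No covariate, model, effect estimate or confidence interval is specified.

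Two other places bear on adjustment:

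- Section 9.3 looks for groups "unbalanced on age, education, income, or other participant characteristics" and continues: "Any variable with an imbalance between the groups at baseline will be examined to determine whether it is related to any of the outcome variables". It then says: "If significant relationships are identified, the variable will be included as a covariate in the models for the affected outcome(s) as a potential confounder".
- Section 2.3.1 says: "Data analysis will use descriptive statistics and general linear mixed models to test the hypotheses". It does not give the terms of those models.

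Baseline values are available. Section 4.1 says "Data will be collected at baseline (Time 1), completion of Phase II (Time 2, 6 months after baseline" and again at 12 months, and the schedules in 1.3 and 8.1 mark every primary biologic outcome at month 0.

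**The concern.** A change score fixes the coefficient of the baseline value at 1. When baseline and follow-up correlate at less than 1 and women are independent, estimating that coefficient gives a more precise contrast. It also removes the part of a chance baseline gap that would otherwise appear in the contrast as regression to the mean. The data for this are already collected, and 40 women per arm leaves little precision to spare.

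The plan also leaves the choice of analysis open. The tests in 9.4.1 cannot take a covariate, so the models in 9.3 have nothing to attach to, and the mixed models of 2.3.1 do not reach Section 9. An analyst trying to honour all three sections would have to choose after seeing the baseline comparison. Whether baseline blood pressure enters the blood pressure analysis could then depend on two significance checks made on the trial's own data.

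**Working it through.** **Inputs.** Effect 6 mmHg and SD 11, from Section 9.2 ("observed a change in systolic BP of 6mmHg (SD \pm 11"), with 11 read as the SD of change. There are 40 women per arm (9.1), or 40 × 0.80 = 32 per arm at the 20% attrition ceiling in 5.5. Assumptions not in the documents: two-sided 5% test, equal variance at both visits, and the correlation ρ, which is shown as a range.

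**The plan's own figure.** Section 9.2 states 70% power. The normal formula gives 68.4% at 40 per arm and the noncentral t gives 67.3%, so the stated figure is reproduced to within 3 points. At 32 per arm the t calculation gives 57%.

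**Precision with independent women.** Let s² be the within-arm variance at one visit.

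- Variance of change: 2s²(1 − ρ).
- Residual variance after baseline adjustment: s²(1 − ρ²).
- Ratio: (1 + ρ)/2, so the saving is (1 − ρ)/2 and the adjusted SD is 11 × √((1 + ρ)/2).

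| Analysis | SD | Variance saved | Power, 40 per arm | Power, 32 per arm |
|---|---|---|---|---|
| Change score | 11 | – | 67% | 57% |
| Adjusted, ρ = 0.3 | 8.87 | 35% | 85% | 76% |
| Adjusted, ρ = 0.5 | 9.53 | 25% | 79% | 70% |
| Adjusted, ρ = 0.6 | 9.84 | 20% | 77% | 67% |
| Adjusted, ρ = 0.7 | 10.14 | 15% | 74% | 64% |
| Adjusted, ρ = 0.9 | 10.72 | 5% | 70% | 60% |

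**Chance baseline gap.** The visit SD is s = 11/√(2(1 − ρ)), the standard error of the baseline difference is s√(2/40), and a gap of that size shifts the change-score contrast by (1 − ρ) times itself.

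| ρ | s | One-SE gap (mmHg) | Shift (mmHg) | Share of 6 mmHg |
|---|---|---|---|---|
| 0.5 | 11.0 | 2.46 | 1.23 | 20% |
| 0.6 | 12.3 | 2.75 | 1.10 | 18% |
| 0.7 | 14.2 | 3.18 | 0.95 | 16% |

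**One church per arm.** Section 6.3 randomizes two churches. Suppose each church has a stable level with variance τ² that is the same at both visits. It cancels in the change score. Adjustment with slope ρ leaves (1 − ρ) of the church difference in the contrast. With n women per arm, and over the draw of churches:

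- Change score: (2/n) × 2s²(1 − ρ).
- Baseline-adjusted: (2/n) × s²(1 − ρ²) + 2(1 − ρ)²τ².

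Setting these equal gives τ² = s²/n for any ρ. The break-even ICC is therefore τ²/(τ² + s²) = 1/(n + 1) = 1/41 = 0.024.

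At ρ = 0.6, s² = 121/0.8 = 151.25. The change-score contrast has variance (2/40) × 121 = 6.05, SD 2.46. The adjusted contrast has variance (2/40) × 151.25 × 0.64 = 4.84 plus 0.32τ²:

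- ICC 0: SD √4.84 = 2.20.
- ICC 0.05: τ² = 151.25 × 0.05/0.95 = 7.96, SD √(4.84 + 2.55) = 2.72.
- ICC 0.10: τ² = 151.25 × 0.10/0.90 = 16.81, SD √(4.84 + 5.38) = 3.20.

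A simulation with a lasting 5 mmHg church difference and no treatment effect agrees. The change score was off by 0.04 mmHg, and the adjusted estimate by 2.5 mmHg at ρ = 0.5 and 1.5 mmHg at ρ = 0.7, close to 5(1 − ρ).

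**The case against.** The strongest objection is that the precision argument comes from trials that randomize individuals. Here women take the assignment of their county's church, and 9.4.1 itself warns of systematic differences between the groups. If those differences are stable, the change score is the better-protected estimate, and the bias in the adjusted one (1.5 to 2.5 mmHg in the example) exceeds the chance shift of 1.0 to 1.2 mmHg. This stands. A reader might infer that baseline adjustment should simply replace the change score, but the design does not support that. A fully stable church effect is itself an assumption; so is its absence.

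Three other strong readings also fail:

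- That the plan rules out adjustment. The wording of 9.3 is broad enough to take in a baseline outcome, and 2.3.1 names mixed models. What is missing is prespecification.
- That the change score is biased by regression to the mean. If arms differ at baseline only by chance, it is unbiased over repeated randomization; the shift is conditional on the gap that happens to occur.
- That a Mann-Whitney test leaves the main trial with no figures in outcome units. Section 9.3 calls for means and SDs of each continuous variable. These are still not a between-arm estimate with an interval.

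Finally, Section 9.1 calls the pilot descriptive and not expected to test the main-trial hypotheses. That lowers the weight of lost power. It does not excuse listing only tests, because a descriptive study of initial efficacy needs estimates with intervals.

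**Conclusion.** The point holds as a gap in prespecification and a conflict among 2.3.1, 9.3 and 9.4.1. Under the independence that the plan's own tests assume, the unadjusted analysis gives up 5% to 35% of the variance for ρ between 0.9 and 0.3. The narrower 15% to 25% needs ρ of 0.7 to 0.5. The documents give no ρ, and it may differ across blood pressure, pulse wave velocity, lipids and glucose.

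The documents also give no ICC, and Section 9.2 says two groups are too few to estimate one for change. Whether adjustment helps or harms therefore cannot be settled in advance: it helps below a stable-church ICC of about 0.024 and harms above it. The defensible position is to plan both estimates and treat neither as the cure.

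**What to change.** In Section 9.4.1:

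- For each continuous outcome, at each follow-up visit where it is measured, prespecify a regression of the follow-up value on arm and that outcome's baseline value. Use the log scale for skewed biomarkers such as triglycerides, hs-CRP and hair cortisol.
- Report the adjusted mean difference with its 95% CI beside the change-score mean difference with its 95% CI, with equal prominence.
- State that neither estimate separates the church effect from the intervention effect, and that both intervals treat women as independent.

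In Section 9.3, take the baseline value of the outcome out of the imbalance-and-significance screen, since it will always be in the regression. Then reconcile 2.3.1, 9.3 and 9.4.1 so that they name the same analysis: either specify the mixed model's terms, including how baseline enters, or delete it.

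The cost is a few sentences and a few lines of code, with no new data and no added burden for participants. The small downside is that the two estimates may disagree if the churches differ stably at baseline. Readers of the pilot should see that disagreement.
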